### **5.1.I. Study Variables**

**5.1.I.a. Screening Interview.** The screening interview will be conducted over the phone and will identify exclusionary variables by self-report that would render participation in a group clinic inappropriate: 1. Substantial hearing or vision loss, such that participation with the materials and group exercises would not be possible. 2. Transportation or availability barriers, such that would prevent the participant from presenting in person on a regular basis. 3. Unwillingness to discuss their health and health care in a peer-group setting. 4. Cognitive functioning. Cognitive functioning will be assessed using a six-item screening tool that has been validated for telephone use. 5. Current active substance abuse. We will administer modules from the MINI, a short structured interview used to identify mental health conditions including substance abuse according to DSM-IV. It is appropriate for telephone screening (Attachment 9 and 10).

**5.1.I.b. Primary Outcomes.** **1. Diabetes Control Measure.** HbA1c is an established measure of diabetes control and a strong predictor of subsequent health outcomes related to diabetes. There is consensus that levels  $>7\%$  should be treated because of their association with both cardiovascular risk and microvascular end-organ damage (e.g., kidney failure). Our eligibility criteria of HbA1c of  $\geq 8\%$  at baseline allows for detection of a clinically significant change without limiting enrollment to only those with very poor control or other selective groups. **2. Diabetes-related Distress Scale (DDS).** DDS, a 17-item instrument that assesses psychological burden specific to diabetes care (see Attachments 7, 8, and 11), has high internal consistency, reliability ( $\alpha = 0.93$ ) and validity with self-care behaviors ( $r = .30, P < .001$ ) and physical activity ( $r = .13, P < .01$ ). DDS scores correlate with HbA1c levels and are a robust measure of other clinically significant diabetes self-management endpoints. Phase 2 study measures and the data collection timeline are outlined in Table 10.

**5.1.I.c. Baseline Covariates.** **1. Patient-Level Characteristics (Self-report):** We will collect date of birth, gender, race, education, living situation [alone or not], social support, VA

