copay status, employment status, and prior receipt of related treatments. **2. Patient-Level characteristics** will be obtained by chart review and from the Corporate Data Warehouse. (Chart review) A trained research assistant will conduct a structured chart review to extract data on relevant weight, body mass index, Deyo comorbidity score, receipt of other related treatments (e.g., diabetes education), and primary care visits in the prior 12 months. (Corporate Data Warehouse) We will ascertain adherence to refills of prescribed medications (medication possession ratios for all diabetic medications including insulin) for enrolled patients. **3. Health System / Clinic Characteristics:** We will collect facility, primary care, and PACT characteristics from the Corporate Data Warehouse to account for potential confounding. **4. Patient self-management knowledge and understanding of diabetes** will be assessed using a validated 13-item measure that has demonstrated adequate internal consistency ( $\alpha = 0.68$ ) and correlation with HbA1c values. **5. Patient-reported measures:** We will assess levels of FHL and patient activation at baseline. These measures will be collected verbally during the randomization call because subjects with limited health literacy may not be able to read or fully comprehend a written measure. These measures will be reported to the EPIC interventionists and blinded for those in the EUC arm. **A) Functional Health Literacy:** We will use three questions developed by Chew et al and the eight question SKILLD survey, developed by Rothman et al (see Attachment 12). They have been validated across multiple VA samples to correlate with expanded measures of health literacy including the Rapid Estimate of Adult Literacy in Medicine (REALM) and Test of Functional Health Literacy in Adults, short form (S-TOFLA). These items require less than three minutes to complete and have been validated among patients with diabetes. **B) Patient Activation:** The Patient Activation Measure (PAM) assesses patients' skill, confidence, and knowledge in managing issues related to their healthcare (see Attachment 12). This 13 item scale can be completed in less than ten minutes. PAM scores have been associated with diabetes outcomes in primary care samples.

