Specific Aim 2: The distributional nature of all variables will be assessed, and nonparametric tests (e.g., Fisher's Exact Test; Mann-Whitney test), data transformations (e.g., log linear), or other alternate methods (e.g., weighted least squares regressions) will be conducted where appropriate. First, we will compare baseline demographic, clinical, and patient-centered variables (including medication use) between EPIC and EUC with chi-square and independent samples t-tests. Variables with p-values  $< 0.25$  will be included as control variables or propensity scores in subsequent models. We will then compare baseline demographic, clinical, and patient-centered variables between those who complete the study and those who do not using chi-square and independent samples t-tests. Outcome analyses at both post-intervention and post-maintenance will be intention-to-treat and will use the multiple imputation procedures Proc MI and MINANALYZE in SAS Version 9.3 to estimate missing observations. We will evaluate the degree of dependency between patients within a given group session, between patients in a given PACT, and between PACTs within each of the five sites (by examining Intra Class Coefficients). It is likely that significant dependency will exist, and if so, we will accordingly take these into account in analyses (i.e., patients will be nested within PACTs which will in turn be nested within sites). Random regression methods using SAS Proc Mixed will be employed to account for clustering of data.

5.6.C.i. H2 Analyses (Effectiveness) We will employ Analysis of Covariance (ANCOVA) to examine treatment differences in outcomes immediately post-intervention (at 4 months). We will conduct two models: one with HbA1c at post-intervention as the outcome and one with DDS at post-intervention as the outcome. Models will include treatment group (i.e., EPIC versus EUC) as a predictor and respective HbA1c and DDS baseline scores and any demographic,

clinical, or patient-centered variables that differed between the study arms at baseline as covariates. We will calculate treatment effect sizes immediately post-intervention.

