5.6.C.ii. H3 Analyses (Maintenance) Analyses for examination of maintenance of treatment effects will be similar to those for immediate treatment effects post-intervention. We will again employ ANCOVA to examine treatment differences in outcomes at the post-maintenance (10-month) assessment. We will conduct two models: one with HbA1c at 10-months as the outcome and one with DDS at 10-months as the outcome. Models will include treatment group (EPIC versus EUC) as a predictor and respective HbA1c and DDS post-intervention scores and any demographic, clinical, or patient-centered variables that differed between the study arms at baseline as covariates. We will calculate treatment effect sizes at the 10-month assessment.

5.6.C.iii. Exploratory Analyses (Implementation and Effectiveness) We will use a mixed-model approach to conduct separate repeated-measures analyses for HbA1c and DDS simultaneously using all three assessment time points. We will employ growth curve analyses using SAS Proc Mixed to examine overall group differences in improvements or decrements in outcomes over the year, maximize participant data, and account for dependency between patients within a given group session, PACT, and site. Conditional models will contain fixed terms for the intercept, treatment (EPIC or EUC), assessment time period, treatment by time period interaction, and previously identified variables that differ between treatment groups. Modeled random effects will include between-patient variation in baseline scores (i.e., the intercept where baseline assessments are scored 0) and variation in the slopes for time. With three assessments, the focus will initially be on linear patterns of change, although we will evaluate the relative fit of a quadratic pattern of change using the likelihood ratio test. These analyses will allow us to examine the immediate impact of treatment at post-intervention as well as retention, improvement, or decay in outcomes post-maintenance period. The treatment effect will assess differences between the two groups at baseline, the fixed effect of time will measure the average change over time in the outcome (collapsing across the two treatment groups), and the time by treatment interaction will indicate whether change over time (in slopes) differs between EPIC and EUC.

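### Covariates for the Aim 2 models, beyond the earlier outcome score, are chosen by baseline EPIC-v-EUC tests at p < 0.25; a short prespecified prognostic list would be modestly more efficient at almost no cost

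*Combined protocol and SAP*

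**What the plan says.** Section 5.6.C (Specific Aim 2) compares demographic, clinical and patient-centered baseline variables between arms with chi-square and t-tests. Variables with p < 0.25 "will be included as control variables or propensity scores in subsequent models".

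- **H2 (5.6.C.i).** The ANCOVA contains treatment, the baseline value of the outcome, and "variables that differed between the study arms at baseline as covariates. We will calculate treatment effect sizes immediately post-intervention".
- **H3 (5.6.C.ii).** The model contains "respective HbA1c and DDS post-intervention scores" and, again, "variables that differed between the study arms at baseline as covariates".
- **Growth models (5.6.C.iii).** These are fitted "simultaneously using all three assessment time points" and include "previously identified variables that differ between treatment groups".

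The 0.25 cut-off is not repeated in 5.6.C.i to iii. The H2 and H3 text enters the variables as covariates and does not mention propensity scores.

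The candidate pool is described in 5.1.I.c ("We will collect date of birth, gender, race, education" and further items by self-report; "weight, body mass index, Deyo comorbidity score" and others by chart review), in the section on predictors and mediators, and in Table 10. Section 5.6.A promises adjustment for baseline covariates but names none. Sections 5.1.A and 5.1.D.iv make the patient the unit of randomization.

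**The concern.** With individual randomization, any baseline difference between arms arises by chance. A p-value for that difference says nothing about whether the variable predicts HbA1c or DDS, and prediction of the outcome is what makes a covariate worth including. The rule therefore admits irrelevant variables and omits strong predictors that happen to be balanced. It also favours variables that are correlated with treatment in this sample, which widens the standard error of the treatment effect.

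Three things in the models for the two primary outcomes stay unsettled until arm data are compared: which variables enter, whether they enter as covariates or through a propensity score, and whether a variable that differed is one with p < 0.25. At stake is some precision in H2, and a primary model that could easily have been fixed in advance.

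**Working it through.** **1. The plan's own figure.** With d = 0.40, 100 per arm and a two-sided alpha of 0.05, z = 0.40 × √(100/2) = 2.83 and power is Φ(2.83 − 1.96) = 80.7%, against 80% stated. Deff = 1 + 11 × 0.0183 = 1.2013, so 100 becomes 120. Then 120/0.85 = 141.2, which rounds up to 142 per arm, or 284 in total. The plan's numbers reproduce.

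**2. What the rule selects.** A chance-only candidate enters with probability 0.25: 2.5 of 10 on average, 6 of 24, 6.25 of 25. The pool is not numbered in the plan; 5.1.I and Table 10 list roughly 25 baseline items.

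**3. The cost of irrelevant covariates.** For a candidate selected by chance, E[z² | p < 0.25] = 2.89. Each one adds about 2.89/(2n) to the R² of treatment on the covariates, and z shrinks by √(1 − R²). At 100 per arm with d on the residual SD:
- 10 candidates: R² = 2.5 × 2.89/200 = 0.036; power 79.3%.
- 25 candidates: R² = 6.25 × 2.89/200 = 0.090; power 77.0%.

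Simulation gives 78.3% and 76.1%.

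**4. Simulation of H2 when some candidates are prognostic.** Assumptions that are not in the documents:
- 24 candidates (12 as a check), 5 of them prognostic.
- The 5 explain 5%, 10% or 20% of total outcome variance.
- The baseline-outcome correlation is 0.5.
- d is on the total outcome SD.
- The comparison list holds 3 of the 5 predictors plus 3 irrelevant variables.

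There were 10,000 trials per setting, with 24 PACTs and the plan's ICC of 0.0183. Site and group-session levels were not modelled. Power (%) at d = 0.40, 24 candidates with mutual correlation 0.2:

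| Per arm | Variance explained | Rule | Prespecified list | Baseline outcome only |
|---|---|---|---|---|
| 120 | 5% | 94.3 | 95.4 | 95.0 |
| 120 | 10% | 94.8 | 96.5 | 95.2 |
| 120 | 20% | 95.8 | 97.8 | 94.8 |
| 100 | 5% | 89.1 | 90.6 | 90.2 |
| 100 | 10% | 90.1 | 92.3 | 90.1 |
| 100 | 20% | 91.6 | 94.8 | 90.5 |

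The loss against the list is 1.1 to 2.0 points at 120 per arm and 1.5 to 3.2 at 100. With independent candidates it is 1.0 to 1.3 and 1.9 to 2.3. With 12 candidates it is 0.6 to 1.8. The Monte Carlo 95% error of these differences is about 0.3 to 0.5 points. With multiple imputation (142 per arm, 15% of outcomes missing, 4,000 trials) the rule gives 94.5% and 95.8%, and the list 95.6% and 97.2%, at 10% and 20% of variance explained.

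**5. The rule against the baseline outcome alone.** With 24 independent candidates, 100 per arm and 5% of variance explained, the rule gives 87.9%. Baseline-only ANCOVA gives about 90%: 0.40/√(1 − 0.25) = 0.462, z = 0.462 × √50 = 3.27, power Φ(1.31). That is a loss of about 2 points. With 12 candidates the rule gains up to 3.0 points.

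**6. Validity.** Type I error of the rule is 3.5% to 5.7% across these settings. The largest value slightly exceeds the Monte Carlo error of 1.96 × √(0.05 × 0.95/10,000) = 0.4 points. The mean null estimate is within 0.003 of zero in the complete-data runs.

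**7. Scale of d.** The powers near 90% arise because baseline adjustment adds power when d is on the total SD. With d on the residual SD and candidates that predict little or nothing, the rule gives about 76% to 79% at 100 per arm, where baseline-only gives 80%.

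**8. Threshold.** If a variable that differed means p < 0.05 (run without clustering, 6,000 trials), the rule gives 94.2 / 94.5 / 95.1% against 94.5 / 94.5 / 94.0% for the baseline outcome alone.

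**The case against.** The rule is a stated algorithm, applied to listed variables without looking at outcomes. Apart from the propensity-score option and the unrepeated threshold, it leaves little room for outcome-driven choice. That stands. A reader might infer that the rule biases the treatment effect or inflates false positives; the documents and the calculations do not support this.

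The power loss is measured against a list that the plan does not contain, built on assumed predictors. That also stands, so the figure has meaning only with its comparator. Against the simplest alternative, the baseline outcome alone, the rule is sometimes better.

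A reader might also take the loss as a threat to the planned 80% power, or take the powers near 90% as reassurance. Neither follows, because the answer depends on which SD standardizes d, and the plan does not say.

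Finally, 5.1.B calls the trial cluster randomized, which might suggest that baseline differences are not pure chance at patient level. The same sentence makes patients the unit of randomization, in agreement with 5.1.A and 5.1.D.iv.

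**Conclusion.** The point holds as a cheap improvement in efficiency. Section 5.6.C picks covariates by chance imbalance where it could pick them by prognostic value, and leaves their form and, for H2 and H3, the threshold open. For H2 at d = 0.40 on the total SD, with 12 to 24 candidates of which 5 explain 5% to 20% of outcome variance, the loss is about 0.6 to 3 points against a list that gets 3 of 5 predictors right. Against the baseline outcome alone, the range is a loss of about 2 points to a gain of about 3. If the threshold is read as p < 0.05, the rule is about level with baseline-only ANCOVA. Validity is not in question. These sizes rest on assumed numbers, strengths and correlations of candidates. H3 and the growth models share the rule but were not quantified, so no figure should be carried over to them.

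**What to change.** Delete the p < 0.25 and propensity-score selection rule. Before any comparison of the arms, name a short list of already-collected baseline variables that the investigators expect to predict HbA1c or DDS, and use it unchanged in every imputed data set.

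- **H2:** the baseline value of the outcome plus the list.
- **H3:** the list in place of the imbalance-selected variables. Which earlier outcome score H3 adjusts for is a separate matter and is not changed here.
- **Growth models:** the list without the baseline outcome, which is already a response there.

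Keep the planned nesting in PACT and site, and keep the baseline comparison as description only.

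The cost is SAP wording and an agreed list; no new data are needed. If the chosen variables predict little, the gain over the rule is about 0 to 2 points. If they predict nothing, a five-variable list gives up about 1 point against the baseline outcome alone (79.1% against 80.2% at 100 per arm, d on the residual SD, 25 candidates). That is a reason to keep the list short.

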**5.1.D.iv. Protocol for Randomization into Intervention Groups.** Enrolled Veterans will be randomly assigned to EPIC or EUC using random numbers generated in SAS PROC PLAN. We estimate that half of the expected sample of 284 veterans will be randomized to the intervention and half will be randomized to the enhanced usual care arm. We will utilize the steps described below in §5.2 and § 5.3 to identify, recruit, consent, and enroll patient participants. With the assistance of PACT staff, un-blinded research staff will coordinate the scheduling of participants to EPIC group intervention sessions and EUC referrals.

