**5.1.H.ii. Data Collection at Follow Up Assessments.** Post-intervention follow up assessments will be targeted for collection at 5-months after the date of randomization, with assessments occurring no earlier than 4 months after randomization and no later than 6 months after randomization. The assessment following the maintenance phase (Figure 3) will be targeted for collection at 10-months after the date of randomization. Self-reported measures at follow up assessments will be collected by central research staff via telephone using a structured data collection tool. To guide completion of the telephone interview, participants will be mailed blank assessment packets for reference. Blinded research staff will be trained to administer questionnaires by telephone at follow-up assessments and to instruct participants on how to accurately respond to questionnaires. A structured guide will steer participants through response options. We have implemented these procedures in previous studies to improve data collection and reduce missing data. Patient assessments will not be audio-recorded during the study.

Study staff, working with PACT clerical staff, will schedule a lab visit for HbA1c within 2 weeks of the target data collection time. When a clinical HbA1c lab value is available within the data collection window, it will be used for the research analysis.

Study staff will also perform chart abstraction of patient-level characteristics and clinical or PACT/facility variables that may account for confounding. The patient-level characteristics will include: weight, body mass index, Deyo comorbidity score, receipt of other related treatments (e.g. diabetes education), and primary care visits in the last 12 months.

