**5.1.H.iii. Attrition/Retention Estimates.** Given the benefits of the computerized patient record and our prior experience with VA participants, we expect that rates of missing data for primary outcomes will be <15%. While we may experience a lower adherence with EPIC group sessions, it is reasonable to anticipate having primary outcomes data for  $\geq 85\%$  of participants, as reflected in our sample size and power estimates. To handle missing data, we will conduct sensitivity analyses using tests for data missing completely at random and tests for nonrandom missingness. These analyses will allow us to evaluate whether the reasons for loss to follow-up at the various time periods are related to the observed values of the outcome variables. Additionally, we will plot the data over time to visually assess changes in outcomes from baseline to 1-year and to indicate whether additional terms are needed in the models to account for nonlinearity over time.

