#### **5.5.B. Data Collection Strategy § 5.1.H.**

#### **5.5.C. Study Variables § 5.1.I.**

### **5.6 Data Analysis**

#### **5.6.A. Sample Size Calculation/Sample size determination**

Sample size is calculated according to the estimated intervention effect size at post-intervention. We then estimate power to detect treatment effects at the post-maintenance (10-month) follow-up as well as power to detect treatment differences in linear change across the three time points for a 3-level cluster-randomized trial with repeated assessments. We will adjust models for baseline covariates of study patients. All tests will be two-sided with an alpha of 0.05. In our recent RCT, differences in HbA1c change between EPIC versus enhanced group education indicated medium treatment effects at post-treatment and at 1-year (Cohen's  $d = 0.48$  and  $0.42$ , respectively). A similar trial revealed a treatment difference between a glucose self-monitoring protocol and an active control group in DDS scores that correspond to large effects of treatment at 1-year (all pre-post  $d$ s  $> 0.80$ ). To capture treatment effects for both clinical and patient centered outcomes in this implementation trial, a conservative small-to-medium effect size of  $d = 0.40$  (which is 16.67% smaller than the effect found for HbA1c in the prior trial) was used to calculate sample size. Assuming no intra-class correlation (ICC) within

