PACTs, 100 patients in each treatment arm (i.e., EPIC and EUC) will allow for 80% power to detect small-to-medium effects and 98% power to detect medium effects ( $d = 0.50$ ). To account for the dependency among patients within a PACT, the Design Effect (Deff) was applied, following the approach of Schnurr et al. The sample size was inflated using the formula,  $Deff = 1 + (n-1)\rho$ , where  $n$  is the average number of patients per PACT and  $\rho$  is the ICC for PACTs. In our preliminary work, we identified an ICC for PACTs of 0.0183, an average of 27 eligible patients per PACT, and expect that an average of 12 patients per PACT will participate, which yields  $Deff = 1 + (12-1) * 0.0183 = 1.2013$ . Applying this adjustment, the minimum number of patients in the clustered design is  $100 \times 1.2013 = 120$  in each treatment group. Further adjusting for a maximum of 15% attrition, 142 patients will be recruited for each treatment group (total  $N = 284$ ). Therefore, the minimum number of PACTs to be sampled for this nested analysis is technically 11.8, (i.e.,  $142/12$ ), which will be rounded up to 24 PACTS. This is highly feasible, representing just 32.5% of the total number of PACTs (75) at all study sites. Treatment group effect sizes as small as  $d = .40$  can be detected with 80% power at 1-year given a total of 284 patients (an average of approximately 12 patients randomized to either EPIC or EUC from within 24 PACTs sampled), even after accounting for maximum attrition and estimated dependency within PACTs. A sample size of 284 participants is adequate for repeated measures analyses as well. Optimal design software estimated power to detect treatment group differences in linear change across all three assessments. Prior data indicated a main effect of treatment (EPIC versus enhanced group education) for linear change in HbA1c of 0.20, and between – and within – PACT variance in linear change of 0.018 and 0.206, respectively. These values indicate a small-to-medium between-groups effect size of 0.42. A total of 284 participants allows for 80% power to detect a slightly larger effect size ( $\delta = .53$ ) for repeated measures analyses of linear change over time. Furthermore, there is 98% power to detect a medium effect size of  $\delta = .75$ .

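### Cheap improvement: near-window HbA1c values in the VA record have no stated role in imputing missing HbA1c outcomes, and could be named as auxiliary variables

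*Combined protocol and SAP*

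**What the plan says.** - **Clinical values.** Section 5.1.H.ii: "When a clinical HbA1c lab value is available within the data collection window, it will be used for the research analysis". The post-intervention window runs from 4 to 6 months after randomization, with a 5-month target. For the post-maintenance assessment only a 10-month target is given, plus lab scheduling within 2 weeks of target; no earliest or latest date is stated.
- **Expected missingness.** Section 5.1.H.iii expects less than 15% missing primary outcomes, citing the computerized record, and concludes that "it is reasonable to anticipate having primary outcomes data" for at least 85% of participants. It also plans tests of the missingness mechanism.
- **Missing-data method.** Section 5.6.C, Specific Aim 2: intention-to-treat analyses "will use the multiple imputation procedures Proc MI and MINANALYZE in SAS Version 9.3 to estimate missing observations". No imputation model, auxiliary variable or number of imputations is listed. Completers and non-completers are to be compared at baseline.
- **Access to the record.** Section 5.2.B.i extracts HbA1c from the Corporate Data Warehouse for screening. Table 10 returns to database pharmacy refills at 4 and 10 months.
- **ANCOVA covariates.** H2 (5.6.C.i) adjusts for baseline HbA1c; H3 (5.6.C.ii) adjusts for post-intervention HbA1c.

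**The concern.** A patient with neither a study draw nor a clinical value in the window goes to multiple imputation. If that patient has a routine VA HbA1c shortly before or after the window, it is likely to be among the strongest predictors of the missing outcome and is direct evidence on how an absent patient fared. The plan is silent about such values.

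Two things are at stake:

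- **Precision.** Information that may already sit in the record is not put to use.
- **Robustness.** If loss depends on glycemic control, imputing without these values requires missingness to be random given less information, which is a stronger assumption than the available data may require.

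A missing post-intervention HbA1c matters twice, as the H2 outcome and as the H3 covariate. With no 10-month limits, whether a late clinical value counts as an outcome or as missing would be settled only once the data are in hand.

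**Working it through.** **1. The plan's own sample size (5.6.A, 5.1.D.iv).** Inputs: "All tests will be two-sided with an alpha of 0.05"; "a conservative small-to-medium effect size of" d = 0.40; 1:1 allocation ("We estimate that half of the expected sample of 284 veterans will be randomized to the intervention"); "we identified an ICC for PACTs of 0.0183"; 12 patients per PACT; 15% maximum attrition.

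- The normal approximation needs 99 per arm. The stated 100 gives 80.7% power, which agrees with the 80% figure in "will allow for 80% power to detect small-to-medium effects and 98% power to detect medium effects". (The 98% there, for d = 0.50, comes out at 94.2%; it plays no part here.)
- Design effect = 1 + 11 × 0.0183 = 1.2013, giving 120 per arm.
- 120 / 0.85 = 141.2, rounded up to 142 per arm, 284 in total. This reproduces the plan.
- With 15% missing, 142 × 0.85 = 120.7 per arm remain. Dividing by 1.2013 gives 100.5, and power is 80.9%. With nothing missing it would be 86.8%.

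**2. Predictive value of a nearby clinical HbA1c.** The documents give no correlations or availability, so these are assumptions: 0.5 between baseline and each later value; r = 0.6 to 0.8 between the missing outcome and the nearby value; availability a = 50 to 90% of missing cases.

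Partial correlation given baseline = (r − 0.5²) / (1 − 0.5²) = (r − 0.25) / 0.75.

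| r | partial correlation | R² |
|---|---|---|
| 0.6 | 0.467 | 0.218 |
| 0.7 | 0.600 | 0.360 |
| 0.8 | 0.733 | 0.538 |

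**3. Gain in effective sample size.** With missing share m, information fraction = 1 − m(1 − R² × a), compared with 1 − m.

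- m = 15%, low: R² × a = 0.218 × 0.5 = 0.109; (1 − 0.15 × 0.891) / 0.85 = 1.019, a gain of 1.9%.
- m = 15%, high: R² × a = 0.538 × 0.9 = 0.484; (1 − 0.15 × 0.516) / 0.85 = 1.085, a gain of 8.5%.
- m = 5%: the same steps relative to 0.95 give about 0.6% and 2.5%.

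Cross-check by the regression-estimator variance, σ²[(1 − R²)/n_obs + R²/n_aux], with n_obs = 142(1 − m) and n_aux = 142(1 − m + m × a). At m = 15% the equivalent n per arm rises from 120.7 to 122.9 (1.8%) or 130.3 (8.0%), and power from 80.9% to 81.6% or 83.8%.

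**4. The 10-month visit.** The H3 ANCOVA already conditions on post-intervention HbA1c, so a compatible imputation model contains it. If that value is observed and correlates 0.6 with both the missing outcome and the nearby record value (assumed), then given baseline those two correlations are each (0.6 − 0.25)/0.75 = 0.467, with square 0.218. The further partial correlation is (0.467 − 0.218)/0.782 = 0.318 at the low end and (0.733 − 0.218)/0.782 = 0.659 at the high end. R² falls to 0.10 to 0.43, and the gain at 15% missing to about 0.9 to 6.9%.

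**5. Bias, if any.** The documents give no figure. As illustration, suppose missing patients in one arm differ from their imputed values by 0.2 to 0.5 SD. At 15% missing the bias is 0.15 × 0.2 = 0.03 to 0.15 × 0.5 = 0.075 SD, or 7.5 to 19% of d = 0.40. When loss depends on the outcome itself, the nearby value removes roughly R² × a of this: 0.109 to 0.484, or 11 to 48% overall. A departure of 0.3 SD gives a bias of 0.045 SD, which would fall to 0.040 or 0.023 SD.

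**The case against.** A reader might infer that the plan discards out-of-window values and that the HbA1c result is therefore biased. The documents do not support this. Section 5.1.H.ii says what happens inside the window and nothing about values outside it. Since 5.6.C lists no imputation model, such values are not expressly excluded, and no dropout bias is demonstrated.

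Other objections also stand:

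- **Availability is unknown.** Extraction of HbA1c is described only for screening, and patients with no value in a two-month window may be the least tested. Table 7 still has clerical staff ordering HbA1c at 6 and 12 months, which must be reconciled with 5.1.H.ii; it does not establish how often nearby values will exist.
- **Other information could inform the imputation.** Refill records and group attendance appear in Table 10, and nothing bars them from the model.
- **Power already absorbs 15% loss**, and 15% is a ceiling rather than an expectation.
- **Values taken before month 4 may fall while sessions are running.** Section 5.1.E.i allows 3 to 6 months for the sessions, so such values may predict the outcome differently in the two arms.

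These points limit the size of the gain and shape the remedy. They do not answer the central point: a potentially strong predictor in a source the study already queries has no stated role.

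**Conclusion.** This is a cheap improvement, not an error that endangers the trial. Under the assumed correlations and availability, using near-window values adds about 2 to 8% to the effective sample size for HbA1c at 15% missing and about 0.6 to 2.5% at 5%. The gain is smaller at 10 months when the post-intervention value is observed. Outcome-dependent dropout bias, if present, would fall by about 11 to 48%. It would be reduced rather than removed, because only patients still tested in VA have such values.

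The stronger argument is robustness: without these values the analysis relies on a stronger missing-at-random assumption than necessary. It would be wrong to conclude that the trial is underpowered on this account, since 80.9% power remains at 15% loss. DDS has no record substitute and is unaffected.

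**What to change.** In 5.6.C, specify the HbA1c imputation model:

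- Impute separately by arm, or include arm interactions.
- Include baseline HbA1c, the other visit's study HbA1c, and the nearest post-randomization clinical HbA1c outside the window, with its timing.
- Use the out-of-window clinical value in the imputation step only. It never replaces the outcome and does not enter the ANCOVA. Post-intervention HbA1c remains a covariate in the H3 ANCOVA, as 5.6.C.ii specifies.

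In 5.1.H.ii, state earliest and latest dates for the 10-month HbA1c so that falling outside the window has a definite meaning. Report, by arm, how many patients with a missing HbA1c have such a value.

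Cost: one further data pull and some programming in Proc MI. No patients or visits are added. Patients without such values gain nothing from the added variable.
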